# 5 Statistical and Analytical Plans

## 5.1 General Statistical Considerations

The treatment groups will be displayed as previous treatment in parent study as well as overall treatment group in OLE study.

In general, all safety and efficacy data will be reported as observed. No imputation will be performed for missing data. Descriptive statistics (n, mean, standard deviation, median, Q1, Q3, minimum, and maximum) will be calculated for continuous data. Minimum and maximum will be presented same number of decimal places as reported/collected, one additional decimal place for mean and median, and two additional decimal places for standard deviation. Ninety-five percent (95%) confidence intervals (CIs) will be calculated for select continuous endpoint estimates.

Categorical data will be summarized using n and percentage based on number of nonmissing values. Percentage will be presented with one decimal place. The number of missing values will be presented as a separate category with no percentage, but only if 1 or more patients are missing data for the summary. Otherwise, all categories will be presented (even if no patients are counted in the category). Counts of zero in any category will be presented without percentage.

Data will be presented on listings by prior treatment group in the parent study, subject ID, assessment (in order collected on CRF, unless specified otherwise), and assessment date. Dates will be presented in format DDMMMYYYY.

Relative day calculations will be [date of interest – relative date + (date of interest  $\geq$  relative date)]. This calculation will result in dates prior to the relative date being presented as negative days, and those occurring on or after the relative date as Day 1 or later, i.e., there will be no Day 0.

Two sets of baseline are defined for applicable endpoints: baseline in parent study (1002-040) and baseline in OLE study (1002-050). The parent baseline values will be directly extracted from parent study database. The baseline for the OLE study is defined as the last non-missing value on or prior to the date of first dose in the OLE.

If last dose of study treatment is missing, then the end of study date or death date, whichever occurs earlier, will be used in its place.

The visit schedules and windows are shown below:

Visit I	Day 1/Week 0	Week 12	Week 24	Week 36	Week 52	Week 64	Week 78/EOT	Week 82/EOS
---------	--------------	---------	---------	---------	---------	---------	----------------	----------------

Confidential

Page 11 of 27

Version 1.3, Dec 04, 2019 Statistical Analysis Plan

Month	0	3	6	9	12	15	18/EOT	19/EOS
Slotted Study Week	EOS Parent	Wk 12	Wk 24	Wk 36	Wk 52	Wk 64	Wk 78	Wk 82
Target Study Day	1	84	168	252	364	448	546	574
Analysis Window	1	[2,126]	[127,210]	[211,308]	[309,406]	[407,497]	[498,562]	[563,∞]
Protocol defined visit Windows	[30 Days, Pre M0]	84±7	168±7	252±7	364±7	448±7	546±7	574±14

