7. TREATMENT OF PATIENTS

7.1. **Description of IMP**

Table 2: Investigational Medicinal Products

| Product Name: | Bempedoic acid |
|--------------------------------|--|
| Dosage Form: | Film-coated tablets |
| Unit Dose: | 180 mg |
| Container/Closure ^a | 100-count bottle with screw on, childproof cap |
| Route of Administration: | Oral, daily, with or without food |
| Physical Description: | |
| | |
| Manufacturer (Fill/Finish): | |
| | |
| | |
| | |
| | |
| | |
| | |
| | |
| | |
| | |
| | |

Study drug should be taken once a day (once every 24 hours) at approximately the same time every day and may be taken with or without food. Patients will fast (no food or drink, other than water) for a minimum of 10 hours prior to collection of all laboratory samples.

Please see Pharmacy Manual for detailed storage requirements and instructions.

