9.2.7. Off Study Drug Period Month 19/EOS (Week 82 +14 days)

Patients will return for a final EOS visit 4 weeks after IMP treatment has been completed (including patients who withdraw from IMP treatment prior to Week 78) to undergo the following assessments and procedures.

- Concomitant medication review
- Assess AEs, SAEs, and potential clinical endpoints
- Weight
- Vital signs
- Clinical laboratory evaluations:
 - hematology, blood chemistry, and urinalysis
 - Basic fasting lipids (TC, calculated LDL C, HDL C, non-HDL C, and TG)
 - ApoB and hs-CRP
 - HbA_{1C}

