9.3. Patient Withdrawal Criteria

9.3.1. Early Withdrawal from the Study

Patients must remain in the study until the last scheduled visit at Month 19 (Week 82) to be considered as having completed participation in the study. Patients must remain in the study through Month 18 (Week 78) to be considered as having completed participation in the treatment portion of the study.

Patients who withdraw from IMP prior to Month 18 (Week 78) for any reason will be asked to continue to be followed for safety assessments, including basic fasting lipids, at clinic visit following the protocol-specified visit schedule (see Appendix 1). The patient must provide consent to be followed in the study after withdrawing from IMP treatment. Protocol procedures to be completed for patients who consent will include those specified at each visit as noted in Schedule of Events (see Appendix 1).

Patients who temporarily withdraw from IMP prior to Month 18 (Week 78) for any reason may restart IMP providing that 1) the patient and the investigator are in agreement regarding this course of action, and 2) IMP can be started as soon as possible. For cases where the patient has been off of IMP for more than 4 weeks, the investigator must contact the medical monitor for approval prior to restarting IMP.

Patients who do not provide consent to continue to return to the clinic for safety assessments will be asked to participate in phone calls from the site at protocol-specified visits (see Appendix 1), or at a minimum at 78 weeks, to collect information on AEs, concomitant medications, and current health status. The patient must provide consent to be contacted by phone by site personnel for the purposes of assessing current AEs and current health status.

The patient's decision to participate in the clinical study is voluntary. Patients may refuse to continue in the study and/or withdraw from participation in this study at any time, for any reason, specified or unspecified, and without penalty or loss of benefits to which the patient is otherwise entitled.

It is the right and duty of the Investigator to interrupt the treatment of any patient whose health or well-being may be threatened by continuation in this study. Such patients should be withdrawn from the study and should not be continued under a modified regimen.

Patients who are withdrawn from the study may not re-enter. The reasons for withdrawal from this study may include:

- Unacceptable AE
- Patient's withdrawal of consent

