## 4 Study Design

## 4.1 Study Design

This is a multicenter OLE study designed to assess the long-term safety and efficacy of bempedoic acid (ETC-1002) 180 mg. All patients will receive open-label bempedoic acid 180 mg for up to 1.5 years after rolling over from the parent study (Study 1002-040) followed by a follow-up period off study drug for 4 weeks. Investigators, site staff, patients, and the study team will be masked to study lipid levels until the Week 12 study visit, after which time lipid values will be made available.

An independent expert Data Monitoring Committee (DMC) will formally review accumulating unblinded safety and efficacy data from this and other ongoing studies of bempedoic acid. A blinded independent expert Clinical Events Committee (CEC) will adjudicate designated clinical endpoints across the program, including all major adverse cardiac events (MACE) and non-MACE endpoints defined as: cardiovascular (CV) death (MACE), non-CV death (non-MACE), nonfatal myocardial infarction [MI] (MACE), nonfatal stroke (MACE), hospitalization for unstable angina (MACE), coronary revascularization (MACE), noncoronary arterial revascularization (non-MACE), and hospitalization for heart failure (non-MACE) using standardized definitions. Any clinical endpoints that meet serious adverse event (SAE) criteria will be reported as SAEs as well as a clinical endpoint.

The study will be conducted at approximately 125 clinical sites in the United States, Canada, Germany, Netherlands, Poland, and United Kingdom. The study will end when the last randomized patient completes their last study visit (last patient last visit [LPLV] for last randomized patient). The estimated overall duration of the study (first patient first visit [FPFV] to LPLV) is approximately 2.5 years.

Confidential

Page 8 of 27

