#### 5.2.8 Study Drug Exposure and Compliance

For each patient, the length of exposure to study drug will be calculated as the number of days from the first dose of study drug to the last dose of study drug, regardless if the patient missed one or more doses of study drug. Length of exposure will be summarized by previous treatment group in parent study and overall in OLE study using descriptive statistics for the safety population.

For each patient, overall compliance (%) will be calculated as: (Total Number of Tablets Dispensed – Total Number of Tablets Returned)\*100/ (Treatment Duration in Days). The number and percentage of patients who were compliant with taking study drug will be summarized by previous treatment group in parent study and overall in OLE study for the safety population for the following categories  $0 - \langle 80\% \rangle \geq 80\%$ .

The study drug administration and compliance data will be listed for each patient.

Confidential

Page 14 of 27

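### A missing last-dose date is replaced by an end-of-study date that is off drug by design, and unreturned tablets count as taken; the error is probably small and does not run in one direction

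*SAP*

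**What the plan says.** SAP v1.3, 5.1 (General Statistical Considerations) says that missing data will not be imputed, and then gives a substitution rule for one date: "If last dose of study treatment is missing, then the end of study date or death date, whichever occurs earlier, will be used". The SAP does not define the end-of-study date for a patient who never attends the EOS visit.

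The EOS visit lies in a drug-free period. SAP 4.1 describes treatment "followed by a follow-up period off study drug for 4 weeks". Protocol 9.2.7 says "Patients will return for a final EOS visit 4 weeks after IMP treatment has been completed", and its title gives the window: "Off Study Drug Period Month 19/EOS (Week 82 +14 days". Patients who stop drug early may stay under observation: under Protocol 9.3.1 they "will be asked to continue to be followed for safety assessments, including basic fasting lipids" on the protocol visit schedule.

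SAP 5.2.8 defines length of exposure as "calculated as the number of days from the first dose of study drug to the last dose of study drug", ignoring gaps. It also gives the compliance formula: "overall compliance (%) will be calculated as: (Total Number of Tablets Dispensed", less the tablets returned, times 100, divided by treatment duration in days. Patients are classed only as below 80% or as 80% and above. There is no upper limit and no rule for tablets that are not brought back. Protocol 7.1, Table 2, gives the pack as a "100-count bottle with screw on, childproof cap".

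**The concern.** The substituted date is one on which, by design, the patient has been off drug for four weeks. Following the rule as written turns washout time into exposure. The same date also sets the end of the TEAE window (30 days after last dose, SAP 3.2.1) and, if treatment duration means first to last dose, the compliance denominator. It may also affect which laboratory values count as on-treatment in SAP 5.4.4, where that period is not defined. The Week 82 visit was added in Amendment 2 to obtain data off study drug, and this rule can relabel part of that period as on drug.

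The compliance formula has a separate weakness. A bottle left at home or lost is indistinguishable from one that was taken, and a value well above 100% is classed as compliant.

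The study's primary objective is long-term safety, so readers will rely on its length of exposure and on the TEAE window.

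**Working it through.** **Reproducing the plan's days.** 78 × 7 = 546 and 82 × 7 = 574, as in the SAP 5.1 visit table. The gap is 28 days, or 4 weeks. The protocol allows +14 days at Week 82, so the latest in-window EOS is day 588. (The SAP table shows ±14 for this visit; I use the protocol's window.)

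**Exposure.** Excess = substituted day − true last-dose day, for a patient whose last-dose date is missing.

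| Case | True last dose | EOS day | Excess |
|---|---|---|---|
| Completer, on schedule | 546 | 574 | 28 days (28/546 = 5.1%) |
| Completer, EOS at end of window | 546 | 588 | 42 days (42/546 = 7.7%) |
| Early stopper, EOS 4 weeks after last dose | 100 | 128 | 28 days |
| Early stopper, followed to Week 82 | 273 | 574 | 301 days |
| Early stopper, followed to Week 82 | 100 | 574 | 474 days |

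**TEAE window.** For the on-schedule completer the limit moves from 546 + 30 = day 576 to 574 + 30 = day 604. AE overview percentages use all patients in the safety population (SAP 5.4.1), so a longer window can add patients with events but leaves that denominator unchanged.

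**Mean exposure.** The documents give no rate of missing last-dose dates. Assume 1% to 10%, at 28 days each:
- 1%: 0.01 × 28 = 0.28 days
- 10%: 0.10 × 28 = 2.8 days, and 2.8/546 = 0.5%
- With about 1300 patients, 10% is 130 × 28/365.25 = 10.0 person-years

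**Person-time.** The Day 120 addendum ends person-time, for a patient without the event, at the earliest of last dose + 30 days, end of study and data cut-off. Leaving the cut-off aside:
- On-schedule completer: min(576, 574) = 574 with the true date and min(604, 574) = 574 with the substituted date, so no change.
- Week 12 stopper followed to day 574: min(114, 574) = 114 against 574, so 460 extra days.

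**Compliance.** The number of tablets dispensed is not stated. Assume the fewest whole bottles covering each dispensing interval: 1 for 84 days, 3 for 280 days and 2 for 182 days, which makes 600 tablets for 546 days. Take treatment duration as first to last dose.

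- Nothing returned: 600/546 = 109.9%, whatever was swallowed.
- 70% taken (382 tablets), 100 lost, 118 returned: (600 − 118)/546 = 88.3%, against a true 382/546 = 70.0%. The patient moves from below 80% to above it.
- Stopped at day 100 with the date known, 400 tablets dispensed, none returned: 400/100 = 400%.
- The same patient with the last-dose date missing and EOS at day 574: 400/574 = 69.7%, classed below 80%.
- Completer who took every dose, date missing: 546/574 = 95.1%. At true 80% (437 tablets): 437/574 = 76.1%.

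The last two lines show the substituted date pulling compliance down, against the effect of unreturned tablets.

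**The case against.** A reader might infer that both rules flatter the drug. The documents do not support that. A later last-dose date can add TEAEs to the primary endpoint, and it lowers compliance. SAP v1.3 itself plans no exposure-adjusted rate; Protocol 12.4 offers one only if appropriate. This part of the objection stands.

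A reader might also infer that every affected patient gains at least 28 days, or that the largest errors fall on patients lost to follow-up. Neither follows. The 28 days applies to patients who attend EOS. After a death the death date caps the substitution, and for a patient lost to follow-up the end-of-study date is undefined, so the excess could be near zero. The 301- and 474-day cases need an early stopper who is still in contact at Week 82. Such a patient should have had EOT procedures on stopping drug (Protocol 9.2.6), and Protocol 9.3.2 requires the last-dose date to be recorded at withdrawal. Sections 9.2.7 and 9.3.2 also describe EOS as 4 weeks after the last dose for early stoppers, which gives 28 days. The long follow-up case rests on 9.3.1.

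There are further safeguards. Blank eCRF fields are not permitted (Protocol 16.3), compliance is assessed at each on-treatment clinic visit after Day 1, and administration and compliance data are listed for every patient, so a value of 400% would be visible. The study is descriptive, and compliance is neither an endpoint nor the basis of an analysis set. Nor is compliance part of the exposure calculation, which ignores missed doses.

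These points limit the size and frequency of the problem. They do not change what the two rules do when they apply.

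**Conclusion.** The point holds, as a correction to two derivations. When the last-dose date is missing, the rule in 5.1 assigns a date that is off drug by design for any patient who attends EOS. This overstates exposure by about 28 days (up to 42 within the window), and by more for an early stopper followed to Week 82. The compliance formula in 5.2.8 cannot distinguish tablets taken from tablets not brought back, and it classes impossible values as compliant.

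The direction of error is mixed: exposure is lengthened, the TEAE window is widened, and compliance is lowered by the first rule and raised by the second. The effect on mean exposure is probably small, at most 2.8 days (0.5%) under the assumed 1% to 10% missing at 28 days each. That range, the 600 tablets and the reading of treatment duration are assumptions. The actual number of patients affected cannot be found from the documents. The change is worth making because it is nearly free and the present rule gives a wrong result whenever an EOS attender's last-dose date is missing.

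**What to change.** In SAP 5.1, replace the rule for a missing last-dose date with a ranked one:

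1. the EOT or IMP-withdrawal visit date, if there is one;
2. otherwise the EOS visit date minus 28 days, if EOS was attended;
3. otherwise the last contact at which dosing was confirmed;
4. in no case later than death.

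Flag each substituted date and report how many there are. Step 2 assumes that EOS was held 4 weeks after the last dose, so it can still overstate exposure for an early stopper followed to Week 82 with no withdrawal visit; the flag makes such cases visible.

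Do not take the earliest of all available dates, and do not let a missed bottle return cut exposure short. Tablets are returned only at Weeks 12, 52 and 78. A completer who forgot the bottles at Week 78 would be set back to day 364, losing 546 − 364 = 182 days of true exposure and every TEAE starting after 364 + 30 = day 394.

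In SAP 5.2.8, compute compliance over intervals that have a returned-tablet count, report how many patients have unaccounted-for tablets, and show values above 100% as a separate class.

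The cost is SAP wording and two derivations, with no new data collection. Exposure and compliance may look slightly less favourable.

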## 5.2 Statistical Analysis Plans

#### 5.2.1 Analysis Sets

#### 5.2.1.1 Safety Population (SP)

The SP is defined as all enrolled patients who received at least 1 dose of bempedoic acid during the OLE period and will be used for demographics and baseline characteristics, treatment exposure, concomitant medications, safety and efficacy summaries. If all subjects receive at least one dose of bempedoic acid in this study, the SP will be used for all efficacy analyses as well.

#### 5.2.1.2 Completer Analysis Set (CAS)

The CAS is defined as the patients who completed the full 78 weeks treatment as per End of Treatment CRF page.

#### 5.2.2 **Protocol Violations and Deviations**

A full list of protocol violations and deviations will be compiled and reviewed by the clinical team to identify key versus non-key violations/deviations before final database lock. For violations at study entry, patients will be assessed against the inclusion and exclusion criteria of the protocol. For on-study deviations, compliance with the protocol will be examined with regard to prohibited therapies, and timing and availability of planned assessments. The final list of protocol deviation will be approved by the study team prior to interim analysis cut of or final database lock, and will be used to generate the protocol deviation summary and listing.

#### 5.2.3 Subject Disposition

The number of patients enrolled, and included in each analysis population, along with IMP and study completion status, will be summarized by the treatment group in parent ETC-1002-040 study and overall. In addition, the number of patients who withdraw from the study and withdraw from study drug will be summarized by discontinuation reason.

Page 12 of 27

#### **5.2.4 Demographic and Baseline Characteristics**

Two sets of baseline values will be defined: baseline of parent study and OLE study. The parent study baseline will be taken directly from the parent study, and the OLE baseline is defined as last non-missing value prior to the first dose of IMP in the OLE study. The following demographic and both baseline characteristics will be summarized using descriptive statistics by previous treatment group in parent study, as well as overall, for safety population:

- Age group (18-40, 41-64, 65-74, and >=75 years), gender, race, ethnicity, region (North America, and Europe), height (cm), weight (kg), body mass index (BMI) (kg/m^2) (< 25, 25 - < 30, ≥ 30 kg/ m^2), systolic and diastolic blood pressure, fasting lipid parameters (TC, LDL-C, HDL-C, non-HDL-C, and TG), apoB, and hs-CRP.
- Cardiovascular risk factors from the parent study: ASCVD (Yes/No), HeFH (Yes/No), baseline statin intensity (derived) (low or moderate, high), eGFR category, tobacco history, alcohol history, history of diabetics, and history of hypertension.
- The baseline estimated glomerular filtration rate (eGFR) categories are: normal: ≥90 mL/min/1.73m^2; mild Renal Impairment: 60-89 mL/min/1.73m^2; moderate Renal Impairment: 30-59 mL/min/1.73m^2, and severe Renal Impairment (15-29 mL/min/1.73m^2).

#### 5.2.5 Subgroup Variables

Subgroups defined by below variables will be evaluated for safety and the LDL-C efficacy endpoint.

- 1) Gender (male vs. female)
- 2) Age (< 65 yrs. vs.  $\geq$  65 yrs. and < 75 yrs. vs.  $\geq$  75 yrs.)
- 3) Baseline CVD risk category (HeFH (with/without ASCVD) vs. ASCVD only)
- 4) Baseline statin intensity (low vs. moderate vs. high)
- 5) Race (White vs. other)
- 6) Baseline LDL category (< 100 mg/dL vs. ≥100 mg/dL) (efficacy only)
- 7) History of diabetes (yes vs. no)
- 8) Body Mass Index (BMI) ( $< 25, 25 < 30, \ge 30 \text{ kg/m}^2$ )
- 9) Region (North America, Europe)

In case the number of patients within a subgroup is too small, e.g. less than 5% of the overall population, the analyses may not be performed or the subgroup levels may be combined.

Confidential

Page 13 of 27

#### 5.2.6 Medical History

General medical history, cardiovascular history/risk factors, previous statin use and statin tolerance history will be summarized by previous treatment group in parent study, as well as overall in OLE study for safety population and presented in a by-patient listing. Where appropriate, terms will be coded using the Medical Dictionary for Regulatory Activities (MedDRA) Version 20.1 or later.

If a patient is entering the study beyond the 30-day rollover window, new medical history that occur between more than 30 days after the end of the parent study and treatment start in OLE study (exclusive) that period will be collected and presented in a by-patient listing.

#### 5.2.7 Concomitant Medications

Concomitant medications are defined as medications that were ongoing at the time of study drug initiation in this OLE study or new medications that started post study drug initiation and within 30 days following the date of the last dose of study drug.

Medications, including lipid modifying therapy (LMT) medications, will be coded using WHO Drug (March, 2017, or later if appropriate). The frequency of use of concomitant medications will be summarized by previous treatment group in parent study, as well as overall in OLE study, for the safety population according to Anatomical Therapeutic Chemical (ATC) class and preferred term. Concomitant medications will be listed for each patient. Concomitant LMT medications will be summarized by ATC class and medication name and listed separately in a similar fashion.

